- Clinical status assessed using ordinal scale on Study Days 1, 3, 5, 8, 11, 15, 22, and 29;
- Change in clinical status using change in ordinal scale from Study Day 1 to Study Days 3, 5, 8, 11, 15, 22, and 29;
- Days of supplemental oxygen or worse (i.e., ordinal score of 5, 6, 7, 8) up to and including Study Day 29;
- Days of non-invasive ventilation/high-flow oxygen or worse (i.e., ordinal score of 6, 7, 8) up to and including Study Day 29;
- Whether a subject who has a baseline ordinal score of 5 requires new non-invasive oxygen use or worse (i.e., ordinal score of 6, 7, 8) during the study up to and including Study Day 29 (incidence);
- Days a subject who has a baseline ordinal score of 5 has an ordinal score of 6 or greater up to and including Study Day 29;
- Days of invasive mechanical ventilation/ECMO or worse (i.e., an ordinal score of 7 or 8) up to and including Study Day 29;
- Whether subject who has a baseline ordinal score of 5 or 6 requires new invasive ECMO use or worse (i.e., ordinal score of 7 or 8) during study up to and including Study Day 29 (incidence);
- Days a subject who has a baseline ordinal score of 5 or 6 has an ordinal score > 6 up to and including Study Day 29;
- Whether a subject is alive and without respiratory failure (ordinal score < 7) at Study Day 29;
- Time (days) to ventilation or death from Study Day 1 up to and including first 29 days of being on study.
- Days of hospitalization from date of admission up to and including Study Day 29.
- Values of C-reactive protein (CRP), ferritin, D-dimer, lactate dehydrogenase (LDH), and fibrinogen on Study Days 1, 3, 5, 8, and 11 (while hospitalized); and Study Days 15 and 29 (if attends in-person visit or still hospitalized).

Safety

- Whether a subject died from Day 1 up to and including Study Day 15.
- Whether a subject died from Day 1 up to and including Study Day 29.
- Whether a subject died from Day 1 up to and including Study Day 60.
- Time (days) to death from Study Day 1 up to and including Study Day 29.

- Whether a subject experienced at least one SAE up to and including Study Day 60.
- Whether a subject experienced at least one Grade 3 or Grade 4 AE up to and including Study Day 60.
- Episodes of early discontinuation or interruption of study product administration.

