5. SAMPLE SIZE CONSIDERATIONS

We have chosen a sample size of 100 per arm for the proof of concept stages. The power can be computed for the Study Day 8 ordinal score on the basis of an odds ratio representing clinical improvement. The odds ratio represents the odds of improvement in the ordinal scale for treatment relative to placebo. The sample size to detect a given odds ratio for 1:1 randomization using a 2-tailed test at level α is given by

$$\frac{12(z_{\alpha/2} + z_{\beta})^2}{\lambda^2(1 - \sum_{i=1}^K p_i^3)}$$

where λ is the log odds ratio, p_i is the overall probability (combined over both arms) of being in the i^{th} category of the K ordinal outcomes, $z_{\alpha/2}$ and z_{β} are the $1 - \alpha/2$ and $1 - \beta$ quantiles, respectively, of the standard normal distribution.

However, to fully understand all aspects of the testing procedure, we have simulated the probabilities of an intervention: a) being declared futile after 50 subjects per arm, b) being declared efficacious after 50 subjects per arm, and c) being declared promising by 100 subjects per arm.

The interim analysis will find an intervention futile if its point estimate for the primary endpoint has an odds ratio <1 . An intervention can be declared efficacious early after 50 subjects per arm if two-sided $p < 0.001$ and $OR > 1$. If the intervention continues to 100 subjects, it will be declared promising if the final p -value is < 0.20 and $OR > 1$, and statistically significant if the final p -value is < 0.05 . More details are provided in Interim Analysis Section.

Table 4 displays the outcome probabilities in the control arm for sample size determination; this uses preliminary unpublished data from the remdesivir arm in ACTT study. The categories of the 8-point ordinal scale are described in Section 3.2.

Table 4: Expected distribution of ordinal outcomes for the control arm at Study Day 8

Severity Outcome	Outcome (%)
1. Not hospitalized, no new or increased limitations on activities	0.0
2. Not hospitalized, but new or increased limitation on activities and/or requiring new or increased home oxygen, CPAP or BiPAP	34.6
3. Hospitalized, not requiring new or increased supplemental oxygen - no longer requires ongoing medical care	1.2
4. Hospitalized, not requiring new or increased supplemental oxygen - requiring ongoing medical care (COVID-19 related or otherwise)	10.6
5. Hospitalized, requiring new or increased supplemental oxygen	17.1

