6. Hospitalized, requiring new or increased non-invasive ventilation or high flow oxygen devices	8.8
7. Hospitalized, on invasive mechanical ventilation or ECMO	24.2
8. Death	3.5

Table 5 provides the probability to detect futility or efficacy given various odds ratios at interim and final analysis based on simulations (with 10,000 replications). An intervention with no effect (an odds ratio of 1)

had 50% chance of stopping at the interim analysis and has only a 10% chance to show promise. An intervention with an odds ratio of 2 has high power to show promise; that is, there is 91% probability that the final p-value will be less than .20 and only a 3% chance it will be stopped at an interim futility test. The powers in Table 5 are slightly lower than what would be determined from the Whitehead formula, because there is some minimal trade-off associated with testing for futility, especially for the alpha=.20 significance threshold. If the primary endpoint is different for a stage, stage-specific power and sample size computations that are relevant to that stage will be included in the stage-specific SAP.

Table 5: Simulated early stopping probabilities at the interim review (n=50/arm), and power calculations for the final study size (n=100/arm) for Study Day 8 Ordinal Score

OR	Probability of stopping for futility or efficacy at interim analysis for a given true odds ratio		Power at full study enrollment (100 active, 100 control)	
	Futility	Efficacy	Efficacy w/ alpha=.05	Efficacy w/ alpha=.20
0.75	0.793	0.000	0.001	0.008
1.00	0.502	0.000	0.026	0.096
1.25	0.260	0.004	0.136	0.329
1.50	0.126	0.014	0.348	0.604
1.75	0.060	0.036	0.581	0.802
2.00	0.028	0.070	0.765	0.913
2.25	0.013	0.119	0.879	0.961
2.50	0.006	0.179	0.939	0.984

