6. GENERAL STATISTICAL CONSIDERATIONS

6.1. General Principles

This is a proof of concept double-blind placebo controlled randomized trial testing a superiority hypothesis where interventions with a two-sided p-value $< .20$ will be declared promising and will be considered statistically significant if the final two-sided p-value is $< .05$. These data will be summarized by treatment (intervention name versus placebo) and when appropriate by baseline ordinal score. Additionally, data will be described according to the appropriate summary statistics, e.g.

- Percentages/proportions/odds ratios for categorical data. For tabular summaries of percentages/proportions, the denominator (e.g., number of subjects in the specified population) will be displayed.
- Means, standard deviation, median, and/or range for continuous data, median and confidence intervals for time-to-event data.

Confidence intervals will be generated; 95% and 80% confidence intervals will be generated for primary and key secondary outcomes. For hazard ratio and odds ratio estimates, Wald confidence intervals will be used. For confidence intervals of proportions for other efficacy and safety outcomes, Blaker confidence intervals will be used.

In general, all tables will have corresponding listings of data presented unless noted otherwise.

When calculating treatment effects (e.g., differences, hazard ratios, odds ratios) from regression modelling, placebo will be used as the reference group. Subjects on interventions will only be compared to control subjects who could potentially have been randomized to that intervention (i.e., they met eligibility criteria for the intervention and are at a site where the intervention was enrolling at the time of the subject's randomization). Analyses of newly added arm(s) will be performed comparing concurrently enrolled control subjects. For any modeling that uses covariates defined in Section 6.4, the category listed last for each variable in that section will be used as the control group for the interaction analysis and covariate-adjusted analyses.

For the time-to-event analyses, the following SAS pseudocode will be used to generate stratum-specific median time to event estimates and confidence intervals and stratum-specific Kaplan-Meier curves.

```
proc lifetest data=dataset plots=(s);
  time timevariable * censorvariable(1);
  test treatmentvariable;
run;
```

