Non-invasive ventilation/high flow-oxygen days or worse will be defined as the number of days where the ordinal score is > 5 up to and including Study Day 29. The total number of days will be the sum of all reported days, regardless of whether the days occur consecutively or in disjoint intervals. For planned gaps between study days, the day of the qualifying Study Day and the days to the next planned Study Day will be included in the total number of days. The Post-Discharge Supplemental Oxygen CRF questions regarding days of non-invasive ventilation or high-flow oxygen will be used for any time period the subject is not hospitalized at the study hospital. See Section 6.5 for the plan for handling subjects who do not have data through Study Day 29 or die prior to Study Day 29.

Duration of non-invasive ventilation/high flow oxygen days or worse will be summarized in a table using medians and quartiles by treatment (Table 37). Bee swarm plots of non-invasive ventilation/high flow oxygen days by treatment will be generated (Figure 20).

The incidence and duration of new Non-Invasive Ventilation/High-Flow Oxygen use or worse will be analyzed by treatment (Table 40). The numerator will include only subjects in category 5 or below at enrollment who change to a category 6, 7, or 8. The denominator will only include subjects with an actual baseline ordinal score of 5 or below at enrollment. The number of subjects reporting new use of Non-Invasive Ventilation/High-Flow Oxygen and the incidence rate along with 95% and 80% CIs estimated using the Blaker method will be reported.

Refer to Table 6 for a list of covariates and subgroup analyses for this endpoint. Refer to Table 7 for imputation methods to be applied to this endpoint.

Invasive Mechanical Ventilation/ECMO

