Ventilator / ECMO days will be defined as the number of days where the ordinal score > 6 up to and including Study Day 29. The total number of days will be the sum of all reported days, regardless of whether the days occur consecutively or in disjoint intervals. For planned gaps between study days, the day of the qualifying Study Day and the days to the next planned Study Day will be included in the total number of days. The Post-Discharge Supplemental Oxygen CRF questions regarding days of ECMO or invasive ventilation will be used for any time period the subject is not hospitalized at the study hospital. See Section 6.5 for the plan for handling subjects who do not have data through Study Day 29 or die prior to Study Day 29.

Duration of Invasive Mechanical Ventilation/ECMO days will be summarized in a table using medians and quartiles by treatment (Table 38). Bee swarm plots of Invasive Mechanical Ventilation/ECMO days, and days hospitalized by treatment will be generated (Figure 21).

The incidence of new Invasive Mechanical Ventilation/ECMO use will be analyzed by treatment (Table 41). The numerator will only include subjects in category 6 or below at enrollment who change to a category 7 or 8. The denominator will include subjects with a baseline ordinal score of 6 or below. The number of subjects reporting new use of Invasive Mechanical Ventilation/ECMO and the incidence rate along with 95% and 80% CIs estimated using the Blaker method will be reported.

Refer to Table 6 for a list of covariates and subgroup analyses for this endpoint. Refer to Table 7 for imputation methods to be applied to this endpoint.

Proportion of Subjects Alive and Without Respiratory Failure at Study Day 29

The proportion of subjects alive and without respiratory failure at Study Day 29 will be defined as the proportion of subjects with an ordinal score < 7 at any time between Day 26 through Day 32 (Visit window for Study Day 29 Visit). The proportion of subjects with respiratory Failure or death at Day 29 will also be provided. These proportions will be presented by treatment along with 95% and 80% Blaker CIs. Treatment differences will be evaluated using a logistic regression and the p-value will be presented (Table 31).

Refer to Table 6 for a list of covariates and subgroup analyses for this endpoint. Refer to Table 7 for imputation methods to be applied to this endpoint.

Time to Mechanical Ventilation or Death up to and Including Day 29

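### Ventilator/ECMO-or-worse days have no planned between-arm estimate or interval, and their pooled median is expected to be 0 in both arms

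*SAP*

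**What the plan says.** SAP Section 3.1.2.2 sets the objective as efficacy compared with the control arm, including ventilator/ECMO use and the incidence and duration of new use through Day 29. Section 3.2 turns this into day counts. One covers all subjects: "Days of invasive mechanical ventilation/ECMO or worse (i.e., an ordinal score of 7 or 8) up to and including Study Day 29". Another is restricted by baseline: "Days a subject who has a baseline ordinal score of 5 or 6 has an ordinal score > 6".

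For the first, Section 8.2.2 states: "Duration of Invasive Mechanical Ventilation/ECMO days will be summarized in a table using medians and quartiles by treatment". This is Table 38, which reuses the Table 36 shell: n, %, minimum, 25th percentile, median, 75th percentile and maximum for each arm. Figure 21 adds a bee swarm plot. The shell has no mean, difference, interval or p-value.

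The second is row 10 of SAP Table 6, and no table shell displays it. The subgroup rows of Table 38 follow Section 6.4.3, which splits baseline score into 5 versus 6 or 7, so the 5-or-6 set cannot be read off.

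For non-invasive support the text goes further: "The incidence and duration of new Non-Invasive Ventilation/High-Flow Oxygen use or worse will be analyzed by treatment". The shell it points to (Table 40), like Table 41 for ventilation, has columns for population at risk, new cases and incidence rate only.

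The day count above 6 also appears in SAP Table 9 and in the shells of Tables 44 and 45. Section 6.8 makes those analyses optional.

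**The concern.** A subject who never scores above 6 contributes 0 days. If fewer than about half of an arm ever score 7 or 8, the arm's median is 0, and two medians of 0 say nothing about the size of an effect. The quartiles and the plot describe each arm, but neither gives a difference with its uncertainty.

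Section 4.1 of the SAP says that estimates from this trial should inform the sample size and endpoint choice of a larger one. For ventilator/ECMO days, Table 38 supplies neither a difference nor a standard deviation, although daily scores are collected while subjects are hospitalised.

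**Working it through.** **Inputs**
- Sample size, SAP Section 5: "We have chosen a sample size of 100 per arm for the proof of concept stages".
- Effect of interest, SAP Section 5: "An intervention with an odds ratio of 2 has high power to show promise".
- Control distribution on Day 8, SAP Table 4: "Hospitalized, on invasive mechanical ventilation or ECMO 24.2" per cent, and 3.5% dead.
- Not in the documents: the share of subjects with any day at score 7 or 8 through Day 29. Anyone at 7 or 8 on Day 8 is already in that share, so Table 4's figure is its floor for the whole control arm. I vary the share.

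**Step 1. Reproduce the plan's own figure.** Shifting Table 4 by an odds ratio of 2 and averaging the arms gives Σp³ = 0.092. In the Section 5 formula with N = 200:

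√[200 × (ln 2)² × (1 − 0.092) / 12] = 2.70

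Power is Φ(2.70 − 1.96) = 0.77 at α = 0.05 and Φ(2.70 − 1.28) = 0.92 at α = 0.20. Table 5 states 0.765 and 0.913, and the SAP says its simulated values lie slightly below the formula. Simulating the interim rules gives 0.763 and 0.909. Table 4 and the odds ratio are therefore being read as the SAP reads them.

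**Step 2. Share at score 7 or 8 on Day 8.**
- Control: 24.2 + 3.5 = 27.7%.
- Active at an odds ratio of 2: odds 0.277/0.723 = 0.383; halved, 0.192; share 0.192/1.192 = 16.1%.
- Relative fall: (27.7 − 16.1)/27.7 = 42%.

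**Step 3. When do the planned statistics leave 0?** With 100 subjects and the SAS default percentile, the median exceeds 0 only if at least 50 subjects have a non-zero count, and the 75th percentile only if at least 25 do. Exact binomial probabilities, with the active share set by an odds ratio of 2:

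| Control share | Active share | Control median = 0 | Control 75th pct > 0 | Active 75th pct > 0 | Both 75th pct = 0 |
|---|---|---|---|---|---|
| 20% | 11.1% | ~100% | 13% | ~0% | 87% |
| 27.7% | 16.1% | ~100% | 76% | 1% | 24% |
| 30% | 17.6% | ~100% | 89% | 4% | 11% |
| 35% | 21.2% | >99% | 99% | 21% | 1% |
| 40% | 25.0% | 97% | >99% | 54% | ~0% |
| 45% | 29.0% | 82% | ~100% | 84% | ~0% |
| 50% | 33.3% | 46% | ~100% | 97% | ~0% |

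The active median is 0 with probability above 99.9% in every row. The 20% row lies below the floor for the pooled control arm. It is relevant only to a subset such as baseline 5 or 6, whose share is not stated.

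**Step 4. What a difference in means would show.** Assume, for illustration, that affected subjects have 3 to 29 days, uniformly: mean 16, variance (27² − 1)/12 = 60.7, mean square 16² + 60.7 = 316.7. At 27.7% versus 16.1%:
- Means: 0.277 × 16 = 4.4 and 0.161 × 16 = 2.6 days, a difference of about 1.9 days.
- Variances: 0.277 × 316.7 − 4.43² = 68.1 and 0.161 × 316.7 − 2.58² = 44.3.
- Standard error: √[(68.1 + 44.3)/100] = 1.06 days. The 80% interval is about ±1.28 × 1.06 = ±1.4 days and the 95% interval about ±1.96 × 1.06 = ±2.1 days.

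Simulated trials with the same durations agree: at 30% versus 18% the mean difference is about 1.9 days, both medians are 0 in 100% of trials, and z exceeds 1.28 in about 68%.

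**The case against.** A reader might infer that the planned result is simply 0 versus 0 and that a drug which nearly halves ventilation would go unseen. The documents do not support that.

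- Table 38 also gives the 75th percentile and maximum. At Table 4's own shares the most likely picture is a positive control upper quartile against 0 in the active arm, in about 75% of trials (0.76 × 0.99).
- Figure 21 shows the whole distribution, and Table 38 is repeated by baseline score. Subjects at baseline 7 are ventilated on Day 1, so the 6-or-7 row is much less dominated by zeros.
- Ventilation as an event is well covered: adjusted odds ratio and risk difference with intervals for survival without respiratory failure (Table 30), incidence with Blaker intervals (Table 41) and Cox models for time to ventilation or death (Tables 42-43).
- Days above 5 in baseline-5 subjects (Table 6 row 7) are summarised in the baseline-5 row of Table 37.
- Descriptive reporting of other secondary endpoints is a legitimate choice in a proof-of-concept trial.

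All of this stands and narrows the point. It does not supply the missing quantity. The event analyses do not estimate days; Tables 30, 41 and 42 also leave out baseline 7. The optional analyses yield p-values and z-scores, not a number of days. They do show that the SAP accepts a comparison of means for these counts, since the Section 6.8 code tests means.

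A reader might also extend the point to oxygen days and hospital days. Nothing supports that: inclusion criteria 1 and 6 (protocol Section 5.1) require hospitalisation and score 5, 6 or 7 at entry, so those counts should not pile up at zero.

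**Conclusion.** The point holds as a reporting gap of moderate size in a secondary endpoint. Ventilator/ECMO-or-worse days have no between-arm estimate or interval that the plan commits to. Their pooled median is expected to be 0 in both arms for control shares up to about 45%; at 50% the control median is 0 in only 46% of trials. Days above 6 in subjects at baseline 5 or 6 have no table, and the duration promised for new non-invasive support is absent from Table 40.

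The zero-median conclusion rests on Table 4, which covers Day 8 only, and on an assumed share through Day 29. The difference of about 1.9 days rests further on an assumed spread of durations and is illustrative. The absence of an estimate depends on neither assumption; it follows from the table shells and Section 8.2.2.

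**What to change.** In SAP Section 8.2.2 and Table 38, keep the quartiles. Add mean days per arm and the difference in means (active minus placebo) with 80% and 95% bootstrap intervals, resampling within treatment arm and baseline ordinal score. Section 6.1 already describes a 1000-sample bootstrap, but for a logistic risk difference, with 95% limits and no stratification. The text therefore needs to name this use, the strata and the 80% limits (the 100th and 900th sorted values, by the same rule).

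Add a row for days above 6 in subjects at baseline 5 or 6, and the same new columns for days above 5 in the baseline-5 row of Table 37.

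Label the Table 38 estimate as days on ventilation/ECMO or dead. Score 8 counts in the endpoint, and SAP Table 7 carries a last score of 7 or above through Day 29, so it is not purely ventilator days saved.

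The cost is SAP wording and a few table columns; no new data are needed. The drawback is that the mean is driven by the minority with long ventilation or death, which is why the quartiles and the plot should stay beside it. Tables 36 and 39 need no change on this ground.

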3.3. Study Definitions and Derived Variables

3.3.1. Definition of Study Day

Study day will be calculated from the first dosing date of study product and derived as follows:

- For post-dose study days: Assessment Date – First Dosing Date + 1
- For days prior to the first dose: Assessment Date – First Dosing Date

Therefore, Study Day 1 is the day of first dose of study product administration. If subjects are not treated with study product, then their Study Day 1 will be their randomization date.

3.3.2. Analysis Visit Windows

The nominal visit as recorded in the electronic data capture (EDC) or within the permitted visit window as specified by the Schedule of Assessments will be used when data are summarized by visit (see [Table 1](#) and [Table 2](#)). Any data relating to unscheduled visits will not be assigned to a particular visit or time point. However, the following exceptions will be made:

- An unscheduled visit prior to the first dose of study product may be included in the calculation of baseline value, if applicable.

Table 1: Clinical Status Study Day Windows

Analysis Visit Day	Nominal Day	Target day	Visit Window
Screening	Screening	-1 to 1	<1
Baseline	Day 1 (Hospitalized)	1	1
Day 3	Day 3 (Hospitalized)	3	3
Day 5	Day 5 (Hospitalized)	5	5
Day 8	Day 8 (Hospitalized)	8	8
Day 8	Day 8 (Discharged)	8	6-10
Day 11	Day 11 (Hospitalized)	11	11
Day 15	Day 15 (Discharged)	15	13-17
Day 22	Day 22 (Discharged)	22	19-25
Day 29	Day 29 (Discharged)	29	26-32
Day 60	Day 60 (Discharged)	60	57-63

Table 2: Lab Sample Collection Study Day Windows

Analysis Visit Day	Nominal Day	Target day	Visit Window
Screening	Screening	-1 to 1	<1
Baseline	Day 1 (Hospitalized)	1	1
Day 3	Day 3 (Hospitalized)	3	2-4*
Day 5	Day 5 (Hospitalized)	5	4-6*
Day 8	Day 8 (Hospitalized)	8	7-9
Day 11	Day 11 (Hospitalized)	11	10-12
Day 15	Day 15 (Hospitalized)	15	14-16
Day 15	Day 15 (Discharged)	15	13-17
Day 29	Day 29 (Hospitalized)	29	28-30
Day 29	Day 29 (Discharged)	29	26-32

*For windows that overlap, the priority will be given to the earlier date. For example, a lab sample drawn on Study Day 4 will be used as a Study Day 3 lab sample draw if there isn't a lab sample drawn for Study Days 2 or 3, regardless of whether a Study Day 5 lab is drawn.

In general, the Study Day 1 (baseline) value will be the last non-missing value prior to the administration of the first dose. If multiple measurements occur on the same day, the last non-missing value prior to first dose will be considered as the baseline value. If these multiple measurements are recorded on Day 1 but the time is

not available, the average of these measurements (for continuous data) will be considered the Study Day 1 value. For categorical measurements, if there are multiple records with the same time or no time recorded on the same day prior to the first dose, the value with the lowest severity will be selected as baseline (i.e., normal will be selected over abnormal).

